## VACCINE REACTION AND ADVERSE EVENT DIARY

**Section 1: Diary - Reactogenicity Days 1-8**

My Subject ID number is \_\_\_\_\_

Date								
Day of immunization ►	Evening of Dose	1 Day after	2 Days after	3 Days after	4 Days after	5 Days after	6 Days after	7 Days after
Symptom	○	○	○	○	○	○	○	○
Body temperature	○	○	○	○	○	○	○	○
Celsius (C) or Fahrenheit (F)								
Fill in today's column by entering the worst grade/severity for each symptom that you have had in the last day (24 hours). Symptom grades are defined at the bottom of the page.								
No Symptoms of Any Kind – Tick this box								
Generalized Symptoms								
Headache								
Fatigue								
Muscle Pain								
Joint pain								
Nausea								
Chills								
Feverish								
Rash (not at injection site)								
Local Reactions								
Pain								
Erythema / redness in mm								
Induration in mm								
Swelling in mm								
In addition, tick the box in today's column if your answer to the question below is YES.								
Any other new symptom(s)? Y or N.								
If yes, describe in section 2.								
Grade 0 =	I didn't have it at all.							
Grade 1 =	I noticed it, but it didn't interfere with my usual activities at all.							
Grade 2 =	I had it, and it was bad enough to prevent a significant part of my usual activities.							
Grade 3 =	I had it, and it prevented most or all of my normal activities, or I had to see a doctor for prescription medicine.							
Grade 4 =	I had to visit the ER or was hospitalized because of the specific symptom							

CONFIDENTIAL

VACCINE REACTION AND ADVERSE EVENT DIARY

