#### **3.2 Endpoints**

##### **3.2.1 Primary Endpoints**

Occurrence of Solicited AEs:

- Solicited administration site reactions (eg, pain, tenderness, erythema/redness, induration/swelling) during the 7-day follow-up period after each vaccination (Day 1-8 and Day 22-29)
- Solicited systemic events (eg, fever, nausea/vomiting, diarrhea, headache, fatigue, myalgia) during the 7-day follow-up period after each vaccination (Day 1-8 and Day 22-29)

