## **7.7.2                   Reactogenicity Assessments**

Subjects will keep a Diary Card to track reactogenicity assessments for 7 days after each vaccination. Reactogenicity assessments include generalized symptoms such as headache, fatigue, muscle pain, joint pain, nausea, chills, fever, and rash (not at injection site), and localized reactions including pain, erythema, induration, and swelling. If an AE continues after 7 days, the AE will be captured as ongoing/continuing (not noted as a new AE).

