**Table 8-1       DAIDS Adverse Events Intensity Assessment**

Grade	Intensity	Definition
Grade 1	Mild	Symptoms causing no or minimal interference with usual social and functional activities with intervention not indicated.
Grade 2	Moderate	Symptoms causing greater than minimal interference with usual social and functional activities with intervention indicated.
Grade 3	Severe	Symptoms causing inability to perform usual social and functional activities with intervention or hospitalization indicated.
Grade 4	Potentially Life-Threatening	Symptoms causing inability to perform basic self-care functions with intervention indicated to prevent permanent impairment, persistent disability, or death.
Grade 5		Any AE where the outcome is death

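### The Diary Card's 24-hour recall on the evening of dosing reaches back before the injection, so pre-dose systemic symptoms can be counted as solicited reactions

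*Combined protocol and SAP*

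**What the plan says.** Section 3.2.1 defines the primary endpoint as "Occurrence of Solicited AEs", local and systemic, within the seven days following each injection. Section 8 likewise starts adverse event monitoring at the first dose. The instrument is the card: "Subjects will keep a Diary Card to track reactogenicity assessments for 7 days after each vaccination" (Section 7.7.2).

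The example card (Appendix A, Diary Section 1) has eight columns, from Evening of Dose to 7 Days after. One instruction covers all of them: complete the day's column by "entering the worst grade/severity for each symptom that you have had in the last day (24 hours". The first column carries no exception, and there is no column for symptoms present before the injection. The appendix allows the example to be adjusted only by adding information.

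The card also has its own severity scale, used in both of its sections:

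- Grade 1: noticed by the subject, with no interference whatever
- Grade 2: "I had it, and it was bad enough to prevent a significant part of my usual activities"
- Grade 3: loss of most or all normal activity, or a visit to a doctor to obtain a prescription
- Grade 4: an emergency room visit or hospitalization

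Section 8.2.3 grades intensity by FDA's 2007 toxicity grading guidance and falls back on the DAIDS scale in Table 8-1 for events the guidance does not cover. Table 8-1 defines Grade 1 as "Symptoms causing no or minimal interference with usual social and functional activities with intervention not indicated"; its Grade 2 begins at anything more than minimal interference.

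**The concern.** A subject who had a headache on the morning of Day 1, before the injection, and who follows the card literally, reports it that evening. It then sits in the first post-vaccination column with nothing to mark it as earlier. That conflicts with the endpoint window, and it can happen at both doses. Because the endpoint is whether an event occurred at all, one such entry is enough to make a subject a case.

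The effect should be similar in both arms, since they are randomized and observer-blinded. Absolute rates are inflated and the contrast with placebo shrinks. For reactogenicity, a contrast pulled towards zero makes the vaccine look closer to placebo than it is.

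The grading issue is secondary. A symptom that interferes slightly fits neither Grade 1 nor Grade 2 of the card, so subjects must choose for themselves, and the split between those grades in any severity table depends partly on that choice.

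**Working it through.** The plan gives no figure to reproduce: Section 9.1 reports no formal sample size calculation and Section 9 no significance testing. The check is on wording and timing, with illustrations on assumed inputs.

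**1. Does the window always reach back before the dose?** Pre-dose hours = 24 − (entry time − injection time). An entry on the evening of the dosing day comes less than 24 hours after the injection, so the result is always positive. The documents give no clock times. Assuming injection between 08:00 and 16:00 and entry between 18:00 and 22:00:

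- 08:00 and 22:00: 24 − 14 = 10 h (42% of the window)
- 10:00 and 20:00: 24 − 10 = 14 h (58%)
- 16:00 and 18:00: 24 − 2 = 22 h (92%)

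**2. What could this do to an occurrence rate?** Let v be the true post-dose rate and b the share of subjects who record a pre-dose symptom in the first column, equal in both arms and independent of v. Then observed rate = 1 − (1 − b)(1 − v), and observed difference = (1 − b) × true difference. All rates below are assumed.

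| True active / placebo | b | Observed active / placebo | Difference in points (true) | Ratio (true) |
|---|---|---|---|---|
| 50% / 20% | 5% | 52.5% / 24% | 28.5 (30) | 2.19 (2.5) |
| 50% / 20% | 10% | 55% / 28% | 27 (30) | 1.96 (2.5) |
| 50% / 20% | 20% | 60% / 36% | 24 (30) | 1.67 (2.5) |
| 30% / 10% | 5% | 33.5% / 14.5% | 19 (20) | 2.31 (3.0) |
| 30% / 10% | 10% | 37% / 19% | 18 (20) | 1.95 (3.0) |
| 30% / 10% | 20% | 44% / 28% | 16 (20) | 1.57 (3.0) |

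For 30 subjects per arm at 50% / 20% and b = 10%, that is 30 × 0.05 = 1.5 extra cases on active and 30 × 0.08 = 2.4 on placebo.

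**3. Which events are exposed?** Injection-site reactions cannot precede the first injection, so dose 1 local results are essentially unaffected. The exposure is in systemic symptoms, at both doses.

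**4. Card against Table 8-1.**

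- Grade 1: the card requires no interference; the table also admits minimal interference.
- Grade 2: the card requires loss of a significant part of activities; the table starts just above minimal. The table therefore has no gap where the card has one.
- Grade 3: the card includes seeing a doctor for prescription medicine; the table already has intervention indicated at Grade 2, and puts hospitalization indicated at Grade 3.
- Grade 4: the card uses an emergency room visit or hospitalization; the table uses loss of basic self-care.

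No section states how a diary grade, or a measurement in mm, becomes the protocol grade.

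**5. Illustration of the Grade 1/2 gap.** If 60% of a 30-subject arm report a systemic symptom and 10% to 30% of those have slight interference (all assumed), 30 × 0.60 × 0.10 = 1.8 to 30 × 0.60 × 0.30 = 5.4 subjects per arm per dose could fall in either grade. The count scales in proportion to the assumed 60%.

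**The case against.** The best reply on the look-back is that pre-dose status is already examined. Table 1-1 schedules a history update, targeted examination, vital signs and oral temperature at both dosing visits. Exclusion criterion 18 covers acute illness or fever in the three days before enrollment, Section 5.4 rechecks for acute illness before dose 2, and subjects are trained on the card. The endpoint definition excludes pre-dose events, and the placebo arm measures the background. This stands in part. It makes b smaller, and it means pre-dose symptoms can be entered, not that they are. But none of these checks is linked to the diary. Diary review (Table 1-1, footnote i) looks for completion and illogical entries, and a headache on the dosing day is not illogical. The placebo arm reveals the background without restoring the diluted contrast.

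On grading, a reader might infer that the gap corrupts the primary result or the safety rules. The documents do not support that. The primary endpoint is occurrence, and a slightly interfering symptom is an occurrence whether entered as Grade 1 or 2. The grade-based criteria in Sections 5.5 and 5.7.2 start at Grade 3 or 4, generally with a relatedness or no-alternative-explanation condition. Section 8.2 gives the intensity assessment to the Investigator, and nothing makes the subject's own grade the protocol grade.

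A reader might also infer that the card contradicts the governing scale. That cannot be shown: Table 8-1 is the fallback, and the content of the FDA guidance is not in the documents.

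Finally, the Amendment 8 summary gives cessation of enrollment as a reason for its changes. Rewording the card would therefore help only the optional Part C, which the protocol still contains.

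**Conclusion.** The look-back is a real defect in the primary instrument, moderate in size and cheap to handle. That the first entry always covers pre-dose time follows from the card's wording alone. How much this matters rests on assumptions: for pre-dose symptom reporting of 5% to 20%, equal between arms, the risk difference shrinks by that same 5% to 20% of its true value and both rates rise. Systemic events at both doses are exposed; dose 1 local reactions essentially are not. It does not invalidate the trial or favour one arm in the raw rates.

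The grading point is secondary. The gap between Grades 1 and 2 is internal to the card and holds whatever scale governs, but it bears on severity summaries only. The differing Grade 3 and 4 anchors are an inconsistency to reconcile, not evidence that any rule was misapplied. The 14-hour figure and the 2 to 5 subjects are illustrations, not estimates.

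**What to change.** **Cards already collected.** Tabulate solicited systemic events twice for each dose and arm: all entries, and without events reported only in the Evening of Dose column. The restricted table also drops genuine reactions that resolved that evening, and keeps any pre-dose symptom that persisted into later columns, so it is a sensitivity display and not a correction. It needs one extra table, provided diary entries are held by day. Report the Grade 1/2 split with a footnote on the card's wording; do not withhold it.

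**Any further use of the card (Part C).** Change the first column's instruction to ask about symptoms since the injection, and note symptoms already present at the existing Day 1 and Day 22 pre-dose checks. The cost is one line on the card and one question at visits already scheduled.

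**Grading.** The sponsor should reconcile Section 8.2.3, Table 8-1 and both sections of the Diary Card, and state how diary grades and mm entries become protocol grades. This review does not choose the anchors. Completed cards cannot be re-graded, so the footnote remains necessary for them.

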**Section 2: Other Adverse Events**

Please describe any other symptoms experienced beyond those listed above. Please describe symptom or diagnosis, severity, start and stop day, if you saw a health care professional and severity below.

Symptom or Diagnosis if visited a Health Care Provider	Did you visit a health care provider	Start Date	Stop Date	Severity 	Comments, including any medicine prescribed or taken to reduce the symptoms

**Please use these qualitative definitions to grade your symptoms:**

Grade 1 =	I noticed it, but it didn't interfere with my usual activities at all.
Grade 2 =	I had it, and it was bad enough to prevent a significant part of my usual activities.
Grade 3 =	I had it, and it prevented most or all of my normal activities, or I had to see a doctor for prescription medicine.
Grade 4 =	I had it and visited the ER or was hospitalized for it.

*Please return this document to your study site.  
If at any time you have questions about completing the diary card, your health, or about the study in general, please contact the study site personnel.*

## **APPENDIX B        POTENTIAL IMMUNE-MEDIATED MEDICAL CONDITIONS**

### **Gastrointestinal Disorders**

- Autoimmune pancreatitis
- Celiac disease
- Crohn's disease
- Microscopic colitis
- Ulcerative colitis
- Ulcerative proctitis

### **Liver Disorders**

- Autoimmune cholangitis
- Autoimmune hepatitis
- Primary biliary cirrhosis
- Primary sclerosing cholangitis

### **Metabolic Diseases**

- Addison's disease
- Autoimmune hypophysitis
- Autoimmune thyroiditis (including Hashimoto thyroiditis)
- Diabetes mellitus type I
- Grave's or Basedow's disease

### **Musculoskeletal Disorders**

- Antisynthetase syndrome
- Dermatomyositis
- Juvenile chronic arthritis (including Still's disease)
- Mixed connective tissue disorder
- Polymyalgia rheumatic
- Polymyositis
- Psoriatic arthropathy
- Relapsing polychondritis
- Rheumatoid arthritis
- Scleroderma, including diffuse systemic form and CREST (alcinosis, Raynaud's phenomenon, esophageal dysmotility, sclerodactyly, and telangiectasia) syndrome
- Spondyloarthritis, including ankylosing spondylitis, reactive arthritis (Reiter's Syndrome), and undifferentiated spondyloarthritis
- Systemic lupus erythematosus
- Systemic sclerosis

### **Neuroinflammatory Disorders**

- Acute disseminated encephalomyelitis, including site-specific variants (eg, noninfectious encephalitis, encephalomyelitis, myelitis, radiculomyelitis)

- Cranial nerve disorders, including paralyses/paresis (eg, Bell's palsy)
- Guillain-Barré syndrome, including Miller Fisher syndrome and other variants
- Immune-mediated peripheral neuropathies and plexopathies, including chronic inflammatory demyelinating polyneuropathy, multifocal motor neuropathy and polyneuropathies associated with monoclonal gammopathy
- Multiple sclerosis
- Narcolepsy
- Optic neuritis
- Transverse myelitis
- Myasthenia gravis, including Eaton-Lambert syndrome

## **Skin Disorders**

- Alopecia areata
- Autoimmune bullous skin diseases, including pemphigus, pemphigoid and dermatitis herpetiformis
- Cutaneous lupus erythematosus
- Erythema nodosum
- Morphoea
- Lichen planus
- Psoriasis
- Sweet's syndrome
- Vitiligo

## **Vasculitides**

- Large vessels vasculitis including: giant cell arteritis such as Takayasu's arteritis and temporal arteritis
- Medium sized and/or small vessels vasculitis including the following:
  - Polyarteritis nodosa
  - Kawasaki's disease
  - Microscopic polyangiitis
  - Wegener's granulomatosis
  - Behcet's syndrome
  - Leukocytoclastic vasculitis
  - Henoch-Schonlein purpura
  - Necrotizing vasculitis and antineutrophil cytoplasmic antibody (ANCA) positive vasculitis (type unspecified)
  - Churg-Strauss syndrome (allergic granulomatous angiitis)
  - Buerger's disease thromboangiitis obliterans

## **Others**

- Antiphospholipid syndrome
- Autoimmune hemolytic anemia

- Autoimmune glomerulonephritis (including IgA nephropathy, glomerulonephritis rapidly progressive, membranous glomerulonephritis, membranoproliferative glomerulonephritis, and mesangioproliferative glomerulonephritis)
- Autoimmune myocarditis/cardiomyopathy
- Autoimmune neutropenia
- Autoimmune pancytopenia
- Autoimmune thrombocytopenia
- Goodpasture syndrome
- Idiopathic pulmonary fibrosis
- Pernicious anemia
- Polyglandular autoimmune syndrome
- Raynaud's phenomenon
- Sarcoidosis
- Sjögren's syndrome
- Stevens-Johnson syndrome
- Uveitis

**APPENDIX C ADDITIONAL ELISA DETAILS**

Name That Appears on Laboratory Report	Vendor	SARs-CoV-2 Antigen	Reporting Status	Intended Use
Anti-SARS-CoV-2 IgG Qual	Euroimmun	Spike (S)	Blinded starting at the Day 1 Visit	It is intended for use as an aid in identifying individuals with an adaptive immune response to SARS-CoV-2, indicating recent or prior infection. At this time, it is unknown for how long antibodies persist following infection and if the presence of antibodies confers protective immunity. This test should not be used to diagnose acute SARS-CoV-2 infection.
SARS-CoV-2 IgG Qual	Abbott Architect	Nucleocapsid (N)	Unblinded throughout the duration of the study	This assay is designed to detect immunoglobulin class G (IgG) antibodies to the nucleocapsid protein of SARS-CoV-2 in serum and plasma from individuals who are suspected to have had COVID-19 or in serum and plasma of subject that may have been infected by SARS-CoV-2.
COVID-19 IgM	Epitope Diagnostics	Nucleocapsid (N)	Unblinded throughout the duration of the study	This test is used as an aid for the detection of novel COVID-19.

CONFIDENTIAL

## KBP-201 Amendment 8 (Final Protocol v9.0, dated 12 November 2021) Updates in FDA Tabular Format

Protocol Section(s) of Current Version (Final Protocol v9.0, 12 November 2021) Affected by Change	Previous Version (Final Protocol v8.0, 28 June 2021) Example Text	Current Version (Final Protocol v9.0, 12 November 2021) Example Text	Rationale
Synopsis (Objectives, Endpoints, Study Design), Sections 3.1.2, 3.2.2, 4.1, 9.6	
Section 9.6 Immunogenicity Analysis
 
The individual sampling and blood collection for ELISA IgG for the spike/anti-RBD and IgM; neutralizing antibody, anti RBD and anti-Fc antibodies will be listed and summarized by time points for each part by treatment.
	
Section 9.6 Immunogenicity Analysis
 
The individual sampling and blood collection for ELISA analysis to determine IgG and IgM antibody titers to the spike RBD and neutralizing antibody titers for parent (Wuhan) and any variant SARS-CoV-2 strains, will be listed and summarized by time points for each part by treatment.
	Clarification of the antibodies to be used for evaluation of immunogenicity.
Synopsis (Study Design), Section 4.1.2, 5.7.1	
5.7.1 Independent Safety Review Committee
 
The iSRC will be asked to review unblinded immunogenicity and safety data when the first 30 subjects vaccinated in the Part A low dose group (including active and placebo subjects) have data available from Day 1 through Day 43 for an assessment of the risk-benefit of the trial.
 
<del>The remaining study cohorts will have an unblinded immunogenicity and safety data review when all subjects in the cohort have data available from Day 1 through Day 43.</del>
	
5.7.1 Independent Safety Review Committee
 
The iSRC will be asked to review unblinded immunogenicity and safety data when the first 30 subjects vaccinated in the Part A low dose group (including active and placebo subjects) have data available from Day 1 through Day 43 for an assessment of the risk-benefit of the trial.
	Due to cessation of subject enrollment, the Day 43 iSRC meeting will not be needed for the Part A high dose and Part B subjects.
Sections 4.1.2, 5.7.1, 6.6.2, 6.6.3.2, 9.5	
4.1.2 Interim Safety Data Review
 
For the interim analysis, treatment codes will only be unblinded by treatment group (not by individual subjects) and only after the data are deemed ready for the analysis and the data has been monitored. The unblinded review will be completed by the iSRC only and the other team members (Sponsor, CRO [except for the unblinded team members preparing the data for unblinded iSRC review], Investigator, and site personnel) will
	
4.1.2 Interim Safety Data Review
 
For the interim analysis, treatment codes will be unblinded and only after the data are deemed ready for the analysis and the data has been monitored. The unblinded review will be completed by the iSRC only and the other team members (CRO [except for the unblinded team members preparing the data for unblinded iSRC review], Investigator, and site personnel) will
	Since there will be no additional subjects enrolled, the Sponsor will be unblinded to treatment while the remaining study team members remain blinded through the end of the study (~1 year).

## KBP-201 Amendment 8 (Final Protocol v9.0, dated 12 November 2021) Updates in FDA Tabular Format

Protocol Section(s) of Current Version (Final Protocol v9.0, 12 November 2021) Affected by Change	Previous Version (Final Protocol v8.0, 28 June 2021) Example Text	Current Version (Final Protocol v9.0, 12 November 2021) Example Text	Rationale
	unblinded iSRC review], Investigator, and site personnel) will remain blinded.	remain blinded until completion of the study. The Sponsor will be unblinded at the interim analysis.	
Synopsis (Statistical Analysis), Section 9.2	
9.2 Analysis Populations
 
Enrolled Population: All subjects who <del>were screened and enrolled to the study. The Enrolled Population will include all screen failures and all subjects who are discontinued from the study prior to study vaccine administration and will be used for disposition summaries.</del>
 
Per Protocol (PP) Population: Includes all subjects in the Safety Population who receive the assigned doses of the study vaccine/placebo according to protocol, have serology results, and have no major protocol deviations affecting the primary immunogenicity outcomes, as determined by the Sponsor before database lock and unblinding. Subjects that are immunized with an approved vaccine will be captured as a subset analysis of the PP Population <del>in six month increments (Days 90-181 and 181-365)</del> based on the date of receiving an approved COVID-19 vaccine.
	
9.2 Analysis Populations
 
Enrolled Population: All subjects who signed the ICF.
 
Per Protocol (PP) Population: Includes all subjects in the Safety Population who receive the assigned doses of the study vaccine/placebo according to protocol, have serology results, and have no major protocol deviations affecting the primary immunogenicity outcomes, as determined by the Sponsor before database lock and unblinding. Subjects that are immunized with an approved vaccine will be captured as a subset analysis of the PP Population at Days 181, 273, and 365 based on the date of receiving an approved COVID-19 vaccine.
	Updates to the analysis population for consistency with the Statistical Analysis Plan.
Synopsis (Statistical Analysis), Sections 9, 9.6	
Section 9.6 Immunogenicity Analysis
 
All derived immunogenicity secondary endpoint parameters: GMT, GMT ratio, GMFR, GMI, and seroconversion rates will be listed and summarized by scheduled time point using descriptive statistics (n, mean, SD, minimum, median,
	
Section 9.6 Immunogenicity Analysis
 
All derived immunogenicity secondary endpoint parameters: GMT, GMT ratio, GMFR, GMI, and seroconversion rates will be listed and summarized by scheduled time point using descriptive statistics (n, mean, SD, minimum, median, maximum,
	Clarification that the immunogenicity secondary endpoint parameters GMT, GMT ratio, GMFR, GMI, and seroconversion rates will need geometric means, CV%, and GeoCV% summarized in addition to the arithmetic mean.

